1.0 Introduction

The overall goal of this study is to minimize negative consequences of Alzheimer's disease and related disorders (ADRD) diagnosis by enhancing the support systems of affected families through the provision of the Options Counseling-Health Education (OC-HE) intervention.

The primary objective is to evaluate the impact of OC-HE intervention on caregivers (caregiver burden) and patients (use of emergency care). The secondary objective is to evaluate the impact of the program through the proposed mechanisms of influence, enhanced social network composition (e.g., network size) and functioning (e.g., social support). In addition, we will assess intervention feasibility and acceptability to better understand intervention impacts and to inform future implementation from the perspectives of the participants, OC-HE interventionist, clinical care staff, and administrator at the Area Agency on Aging.

2.0 Brief Overview of the Study Protocol

The study protocol, presented as an appendix, provides a scientific rationale of the proposed investigation. A brief overview of the study protocol is presented here.

This is a Stage 1 intervention study based on the NIH Stage Model for Behavioral Intervention Development. We aim to enroll 106 family members of individuals newly diagnosed with dementia (PWD); 53 in each of the two group. Participants will be Iowa residents who provide support to a PWD who received diagnosis within the past 6 months. We will recruit adults ages 18 years and older, both males and females, who are not limited cognitively or physically to consent to study participation, to participate in interviews, and to receive intervention.

All participants will be recruited through the University of Iowa Hospitals and Clinics. Three clinics have agreed to facilitate the recruitment: Geriatric Assessment Clinic, Memory Disorder Clinic, and Adult Psychiatry Clinic. Clinical staff members will identify potential participants and either obtain permission for research staff to contact them or provide study and contact information of the research staff for them to contact us. We will not recruit participants outside of the United States. After consenting and completing the baseline interview, participants will be randomly assigned to either OC-HE intervention group or usual care control group.

The intervention consists of two parts, Options Counseling (OC) and Health Education (HE). The OC part includes family assessment, counseling and provision of emotional support, access assistance, and development of independent-living plans (care plans) using the Iowa's Heritage Area Agency on Aging database. The Options Counselor is trained to use motivational interviewing techniques to develop family care plans, provide emotional support, and connect families to available services and programs in the community. The HE part includes post-diagnosis family education using the 7-module health education toolkit developed specifically for this study based on the literature and expert reviews. OC-HE will conduct initial assessment to determine educational needs within 2 weeks of participant's randomization into the intervention group and develop initial care plan; and will conduct 5 monthly follow-up calls to adjust the care plan and provide educational components appropriate at each point. This intervention aims to create direct links between the medical clinics, home and community-based services (HCBS), and family.

Participants assigned to the usual care control group will participate in baseline, as well as 3- and 6-months

follow-up surveys. Those in usual care group will receive a general informational brochure from the Alzheimer's Association, and will be given an option of receiving a call from their local Options Counselor after completing the 6-month survey.

Study duration is about 18 months. We aim to start participant enrollment in August, 2019, complete recruitment by September, 2020, and complete data collection by March 2021. Each participant will be enrolled in this study for about 6 months from enrollment to final interview.

4.0 Study Flow Diagram

Figure 1: Study Flow Diagram

5.0 Recruitment and Retention

Sample

Between June 2015 and May 2016, the 3 UIHC clinics served about 17,500 people with dementia and 657 were newly diagnosed. Power calculations were performed under the assumption of reaching about 12% of newly diagnosed individuals, 106 people; assuming a 25% attrition rate, this will lead to 80 people (40 per group). This will give us about 84% power to detect a 4-point decrease in Caregiving Burden at each 3-month period. Assuming some people may not meet the inclusion criteria, we anticipate screening around 138 potential participants including women and minorities to reach target enrollment size.

Participants

Family participants/caregivers will be family members or friends (e.g., biological and non-biological relatives, friends) who likely will coordinate care and support for the individual who received dementia diagnosis at one of the three participating clinics: Memory Disorder Clinic (Neurology), Geriatric Medicine Clinic (Family Medicine), and Adult Psychiatry (Psychiatry) at the University of Iowa Hospitals and Clinics (UIHC). Potential family participants/caregivers will be referred by the clinical care team members by reviewing EMR in EPIC and identifying patients who have been diagnosed with Alzheimer's or other dementia within the past 6 months. All participants will be asked to participate in a baseline survey and follow-up surveys at three and six months regarding their sociodemographic characteristics, Home and Community-Based Services (HCBS) use and knowledge, caregiving self-efficacy, caregiving preparedness, social support and networks, and their physical and psychological well-being. After completing the baseline, participants will be randomized into either the Options Counselor-Health Educator (OC-HE) intervention group or the standard care (control) group. Participants in the OC-HE intervention group will receive intervention after completing the baseline survey. All consents and interviews will be conducted by the trained research staff from the University of Iowa. Prior to enrolling

participants for the randomized trial, three to five individuals who have family members with dementia diagnosis will be asked to help with pilot testing program materials by providing feedback on the program contents and implementation procedures.

In addition to family participants, **staff participants** (i.e., clinical care team members, interventionist, and administrators of the Heritage Area Agency on Aging) will be asked to complete program logs and exit interviews at the end of the project to provide feedback on the intervention materials and comment on the feasibility and recommendations to improve the program. We expect one person from each clinic/organization to participate in this part of the study with an estimated number of 5 staff participants.

Consistent with the current OC protocol, PWD may choose to participate in any part of the intervention with the family member. Although assessments will be based on participating individuals' reports, we will incorporate patients' perspectives through the Health Education module that guides families to effectively discuss and include perspectives of the patient and all family members when developing and adjusting care plans.

Recruitment

All participants will be recruited through the University of Iowa Hospitals and Clinics: Geriatric Assessment Clinic, Memory Disorder Clinic, and Adult Psychiatry Clinic. We will not recruit participants outside of the United States.

Clinical teams led by project collaborators (Drs. [name], [name], and [name]) will review electronic medical records (EMRs) and use their existing knowledge of the patient to determine which days a diagnosis may be made. For those patients who have been diagnosed within the past 6 months from the beginning of the study, who are eligible for the study, the research team will be notified by clinical teams when those patients and their caregivers will be at the clinic for a visit. On the identified days, a member of the research team will be present at the clinic. In this case, the clinical team members will notify the research team about cancellations and last minute appointments. If a research team member cannot be present due to logistical difficulties, the clinical staff will give study flyer to the potential participants. If the potential participant indicates interest, a potential participant packet that includes the flyer, a consent letter, and study information sheet will be handed out. If the potential participant gives permission for research staff to contact them, the potential participant will be asked to fill out a contact form indicating their name and phone number or e-mail address that will be sent to the research staff from the clinical team staff. If the potential participant does not wish to provide contact information, they will be asked to call the research office indicated on the flyer.

There is no signed consent document for this study. There is a consent letter that interviewers will read through with the participant before the baseline interview begins. Since the study has rolling enrollment, caregivers will have up until the last 6 months of the study to participate (to allow participants enough time to receive the entire intervention). Eligibility will be confirmed by the research assistant before reading through the consent letter with the participant.

Anticipate Accrual Rate

- 25% of planned enrollment (26 participants) recruited by 09/30/2019

- 50% of planned enrollment (53 participants) recruited by 01/31/2020
- 75% of planned enrollment (80 participants) recruited by 04/30/2020
- 100% of planned enrollment (106 participants) recruited by 08/15/2020

Participant Retention

Research staff and the OC-HE will make up to 3 phone calls, at least three days apart, leaving a message if possible to schedule each encounter. On the 3rd phone call, the research staff or OC-HE will let the participant know that they are welcome to contact the research team if they would like to stay enrolled in the study. The participant will have up to 1 month to call back after the 3rd phone call before they are dropped from the study. To facilitate retention, participants will receive \$20 incentives after completing each survey (baseline, 3-, and 6-month follow-up), and the OC-HE will ask participants about how they are feeling about the program and what can be done to support their continued participation in the intervention at each follow-up encounters.

Participant Incentives

At the end of the baseline interview, participants will fill out the reimbursement form, which collects the participant's name, address, and citizenship status. At the end of the baseline, 3 month, and 6 month interviews, the research assistant will send the information to University of Iowa Shared Services, who will process a \$20 check to be sent to the address provided by the participant. The total compensation for the entire study is \$60 per participant. If the participant completes at least 51% of the interview questions, they will receive the \$20 compensation for that interview. To minimize coercion or undue influence, the level of incentive has been capped at \$20 per interview. All participants will be informed during the consent procedure that their participation in this study is completely voluntary, they can stop at any time, deciding not to participate will not impact the services they may receive at UIHC.

Correcting Retention Problems

If the study team encounters retention problems, the PI and Co-PI will meet with the DSMB, clinical staff, interventionist, and research team members to address retention issues. The National Institute on Aging provides recruitment and retention tips in its Recruitment and Retention Tips document, which will be revisited at that time.

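### The 12% reach in protocol section 5.0 does not match 106 of 657 (16.1%), and the documents disagree on intervention length (6 or 3 months) and diagnosis window (6 or 24 months)

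*Protocol*

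**What the plan says.** **Recruitment share.** Protocol section 5.0 (Sample) reports that from June 2015 to May 2016 "the 3 UIHC clinics served about 17,500 people with dementia and 657 were newly diagnosed". It continues: "Power calculations were performed under the assumption of reaching about 12% of newly diagnosed individuals, 106 people". Then, "assuming a 25% attrition rate, this will lead to 80 people (40 per group", which is said to give about "84% power to detect a 4-point decrease in Caregiving Burden at each 3-month period". On screening, "we anticipate screening around 138 potential participants including women and minorities to reach target enrollment size". The 106 recurs in section 2.0, in the accrual targets of section 5.0, and as 53 plus 53 in section 8.0.

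**Intervention length.** Protocol sections 2.0 and 7.0 and the glossary in Appendix A describe an initial assessment followed by five monthly calls. Section 7.0 calls the whole a six-month period. Section 5.0 closes enrolment for the last six months of the study so that late entrants can receive all of it. The SAP, titled a revised plan and dated January 2022, describes an initial telephone session followed by two monthly calls and labels this a three-month intervention. It attributes the move from home visit to telephone to the pandemic. It also lists eight modules, one of them on the pandemic, where the protocol has seven. It does not say that the length or the number of calls was changed.

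**Diagnosis window.** Protocol sections 2.0, 5.0 (Participants) and 5.3, and the first interviewer script in Appendix V, require a diagnosis within 6 months. The screening form in Appendix B asks about 24 months. Section 5.1 names that form as the tool for checking eligibility.

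**The concern.** A percentage and a head count are presented as the same quantity, and on the one base supplied they differ by 27 people. A reader cannot tell what share of newly diagnosed families the study had to enrol. This matters in a trial that logs reach in order to inform later implementation.

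The other two points are independent of the percentage. The length of the intervention decides whether month-6 outcomes measure its effect at completion or its persistence about three months later. It also decides how to read the SAP model that relates baseline-to-month-3 change in network functions to month-6 outcomes. For the OC-HE arm, that change spans the whole intervention on the SAP's description and about its first half on the protocol's. The diagnosis window decides who is in the trial: a form that accepts older diagnoses lets in people outside the stated population, and section 11.0 lists randomising an ineligible participant as a deviation.

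**Working it through.** **Inputs**, all from protocol section 5.0 (Sample): 657 new diagnoses in 12 months; reach 12%; enrolled 106; attrition 25%; retained 80 (40 per group); screened 138.

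**1. The attrition step reproduces.** 106 × (1 − 0.25) = 79.5, about 80, and 80 / 2 = 40 per group.

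**2. The reach step does not.**
- 0.12 × 657 = 78.8, about 79 people, against 106 stated: a gap of 27, too large for rounding.
- 106 / 657 = 16.1%. The ratio 16.1 / 12 is 1.34, so the required share is about a third higher than written.

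**3. Which count fits 12%?**
- Screened: 138 / 657 = 21.0%.
- Enrolled: 106 / 657 = 16.1%.
- Retained: 80 / 657 = 12.2%.

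Only the retained count fits.

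**4. Could another period supply the denominator?** Assume a constant 657 a year, or 657 / 12 = 54.75 a month. Section 2.0 says "Study duration is about 18 months"; less the closed last six months, that leaves 12 months of enrolment. It also says "We aim to start participant enrollment in August, 2019, complete recruitment by September, 2020". With the section 5.0 target of full enrolment by 15 August 2020, those dates span 12.5 to 14 months.

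| Period counted | Months | Diagnoses | 106 as a share |
|---|---|---|---|
| 18-month study less last 6 | 12 | 657 | 16.1% |
| Stated recruitment dates | 12.5 to 14 | 684 to 767 | 15.5% to 13.8% |
| 12 to 14 months plus full 6-month look-back | 18 to 20 | 986 to 1,095 | 10.8% to 9.7% |

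For 106 to be 12%, the pool must be 106 / 0.12 = 883 diagnoses, and 883 / 54.75 = 16.1 months. That is 16.1 − 14 = 2.1 to 16.1 − 12 = 4.1 months of look-back on top of the enrolment window. The documents state no such period.

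**5. Intervention length, side by side.**
- Protocol: initial visit, five monthly calls, six months. Month 3 is about halfway and month 6 is the end.
- SAP: initial call, two monthly calls, three months. Month 3 is the end and month 6 is about three months later.

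**6. Diagnosis window, side by side.** Someone whose relative was diagnosed more than 6 but not more than 24 months ago answers yes on the Appendix B item and fails inclusion criterion 2 in section 5.3.

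**The case against.** **On the percentage.** The sentence says 12% of newly diagnosed individuals, not 12% of the 657. The 657 is a count from 2015–2016, while recruitment was planned for 2019–2020 and also takes in patients diagnosed in the six months before the study began. The shares above run from 16.1% to 9.7%, which brackets 12%. Section 2.0 adds that "The study protocol, presented as an appendix, provides a scientific rationale of the proposed investigation"; that document was not available and may give another denominator. Operational targets are set as counts, and no decision rule uses the percentage. All of this stands. What is shown is a figure that does not reproduce on the only base given, not a proven mistake. It remains that no stated period yields 12%.

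**On length.** The SAP is the later, revised document and refers to pandemic changes, so the difference may reflect a change made after the protocol was written. Within the SAP the timing is clear. Its network model names no treatment arm, so reading the month-3 change as change over the intervention applies to the OC-HE arm only. These points stand too, but the documents do not record a change of length or calls.

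**On the window.** Clinic teams refer patients on the 6-month rule, so the form is a second filter. That limits the likely effect but does not remove the contradiction.

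**Stronger readings.** A reader might infer that the trial is underpowered, because 12% of 657 leaves 78.8 × 0.75 = 59 completers. The documents do not support this: 106 is repeated throughout as the target, and the stated power rests on 40 per group. A reader might also infer that 12% was meant for the 80 retained, that the SAP's schedule is an error, or that ineligible people were enrolled. None of these is stated.

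**Conclusion.** The point holds on three counts, all of modest weight.

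1. Against 657, the stated 12% should read 16.1%, or else rests on a denominator that is not given. This assumes that 657 is the intended base; the look-back variants also assume a constant diagnosis rate. The enrolment target, the retained number, the group size and the stated power do not change, and no loss of power is shown.
2. The protocol and the later SAP differ on the intervention: six months with five follow-up calls against three months with two. The SAP explains the change of mode but not this difference. It alters what month 6 measures. Nothing here says which schedule is right.
3. The screening form and section 5.3 differ on the diagnosis window, 24 months against 6. This is an eligibility contradiction in its own right, whether or not a look-back belongs in the denominator.

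**What to change.** - **Section 5.0:** either state the share as about 16% of 657 for the 106 enrolled, or name the denominator and period that make 106 equal 12% (about 883 diagnoses, or about 16 months at 657 a year).
- **Intervention:** reconcile protocol sections 2.0 and 7.0 and the Appendix A glossary with the SAP overview on length and number of calls. Record any change, with its date and reason. State whether the month-6 assessment falls at the end of the intervention or about three months after it, and interpret the month-6 outcomes and, in the OC-HE arm, the baseline-to-month-3 change accordingly.
- **Eligibility:** reconcile the Appendix B form with section 5.3.

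The cost is wording and a record of any change. No enrolment is added, and the planned numbers stay as they are. Against 657 the stated reach becomes less favourable (16% instead of 12%); if a full 6-month look-back were the intended base it would become more favourable (about 10% to 11%).

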8.0 Randomization

We will use a randomization scheme with a 1:1 ratio based on computer generated random numbers to assign the family to one of the two study arms. We plan to have 53 in the standard care (control) group and 53 in the intervention (experimental) group. Randomization will occur after baseline assessment. The Project Investigator and Co-Project Investigator will be responsible for handling any randomization errors.

Research Manager [name] will be responsible for maintaining the master randomization list, assigning randomization codes, notifying appropriate study staff. [name] will contact the OC-HE with the name and contact information of participants who have been assigned into the intervention arm.

We plan to maintain the assigned and blinded randomization code in an automated, computerized log that is separate from the study data

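### The primary objective has two unranked outcomes, with burden powered at two times, but no primary contrast, primary time, alpha or success rule, so its overall error rate and power are undefined

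*Protocol*

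**What the plan says.** Protocol section 1.0 puts two outcomes under one primary objective: "The primary objective is to evaluate the impact of OC-HE intervention on caregivers (caregiver burden) and patients (use of emergency care". Section 7.0 repeats the intention to look at emergency or urgent service use by the person with dementia, but gives no event rate, effect or power for it.

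Section 5.0 (Sample) contains the only power statement: "This will give us about 84% power to detect a 4-point decrease in Caregiving Burden at each 3-month period". It rests on 106 enrolled and, "assuming a 25% attrition rate, this will lead to 80 people (40 per group". Section 8.0 plans equal allocation: "We plan to have 53 in the standard care (control) group and 53 in the intervention (experimental) group". On timing, section 5.0 says: "All participants will be asked to participate in a baseline survey and follow-up surveys at three and six months". Neither follow-up is named as primary.

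The SAP's Revised Data Analysis Plan fits a separate generalised linear model to each caregiver or patient outcome, with social-network composition and function as the independent variables. Its follow-up analyses model support within caregiver and network-member pairs. It describes no comparison between randomised arms and gives no primary time, significance level or multiplicity rule.

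**The concern.** A randomised trial with a stated primary objective should let the reader say in advance which result would meet it. Here several results could: burden at 3 months, burden at 6 months, or emergency care. Nothing says whether one is enough or all are needed. The first rule raises the chance of a false positive claim and the second lowers power, so the choice matters and should not be open when results are seen.

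The power sentence adds a second ambiguity. It describes "a 4-point decrease in Caregiving Burden at each 3-month period" without saying whether this is a change within a group or a difference between arms. Only the between-arm reading answers the objective, and the two readings need quite different variability to reach 84%. A reader could also take 84% as the power of the primary objective as a whole, although emergency care has no power figure at all.

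**Working it through.** **Inputs from the documents.** 106 enrolled, 53 per arm, 1:1; 25% attrition; 40 per arm analysed; a 4-point effect; power about 84%; follow-up at 3 and 6 months.

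**Inputs not stated, so assumed.** Alpha 5%, two-sided; the SD of burden (back-solved, then varied); correlations between repeated scores (varied).

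**1. Attrition.** 106 × 0.75 = 79.5, about 80. This step reproduces.

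**2. What the 84% requires.** The figure can be neither reproduced nor refuted without an SD and alpha, so solve for the SD. For an unadjusted comparison at one time, normal approximation:

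SD = 4 / [√(2/40) × (1.960 + 0.994)] = 4 / (0.2236 × 2.954) = 6.06

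The t distribution with 78 degrees of freedom gives 5.98, a standardised difference of 4/5.98 = 0.67. Other readings:
- One-sided 5%, between arms: SD 6.78 (normal approximation).
- Within one arm, paired, n = 40: SD of change = 4 × √40 / 2.954 = 8.56 (8.35 by t).

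Between-arm power for 4 points at one time, unadjusted, two-sided 5%, by t: SD 6, 84%; SD 7, 71%; SD 8, 60%; SD 10, 42%.

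**3. If any single win at 5% counts.**
- Two independent tests (burden once, emergency care once): 1 − 0.95² = 9.75%.
- Three independent tests (burden at 3 and 6 months, emergency care): 1 − 0.95³ = 14.3%.
- Three tests, simulated with the two burden tests correlated: 14.1% at a correlation of 0.3, falling to 11.7% at 0.9.

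**4. If alpha is split instead.** Start from 84% at 5%, normal approximation:
- Two tests at 0.025 (critical value 2.241): Φ(2.954 − 2.241) = 76%.
- Three tests at 0.0167 (critical value 2.394): Φ(2.954 − 2.394) = 71%.

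**5. If all must win.** Type I error is not inflated. With 84% for burden at each time, power for both times is 0.84² = 71% if the tests are independent, and about 80% at a correlation of 0.9. Requiring emergency care as well can only lower this. By how much cannot be computed, because no rate or effect is given.

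**6. Power under a baseline-adjusted model over both follow-ups.** Assume one SD and one correlation r among the baseline, 3-month and 6-month scores. The mean of the two follow-ups has variance SD² × (1 + r)/2, and adjusting for baseline removes r² × SD². The variance factor is therefore (1 + r)/2 − r², and the SD at which 84% holds is 5.98 / √factor:
- r = 0.3: factor 0.56, SD 8.0.
- r = 0.5: factor 0.50, SD 8.5.
- r = 0.7: factor 0.36, SD 10.0.

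At an SD of 10, power under this model is about 66% to 84% for r from 0.3 to 0.7, against 42% for the unadjusted single-time test. The SD condition of about 6 therefore belongs to the simple test only.

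**The case against.** The strongest reply is that undefined is not the same as wrong, and this stands. A reader might infer that the trial's claimed error rate and power are false. Neither document states an alpha, so no error rate is claimed. The 84% is stated for burden alone and is correct if the SD is about 6 under the simple test at two-sided 5%.

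A reader might also infer that the chance of a false primary claim is certainly well above 5%. That needs each test to be run at 5% and any one win to count as success, and no success rule is given. Nor do the documents support a figure of 18.5% (1 − 0.95⁴). It counts emergency care at two times, while section 6.1 says only that use of medical services comes from the medical record, and no analysis times are set for it.

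Three further points carry weight:
- The 4-point decrease per period could mean a rate of change from one longitudinal model. That would be a single burden test, and neither SD in step 2 would apply.
- Section 2.0 refers to a study protocol presented as an appendix. It is not in the text available here and may hold the SD, alpha and model.
- Section 2.0 calls this a Stage 1 study, so confirmatory standards apply less strictly, and fixed-sequence testing is one option among several.

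These points limit what can be concluded, but they do not supply the missing rule. The revised SAP is the natural place for it and contains no comparison by arm.

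**Conclusion.** The point holds as a gap in definition. There are two unranked outcomes under the primary objective, burden is powered at two times, only burden has a power figure, and no contrast, primary time, alpha or success rule is given. The overall error rate and the power of the primary objective are therefore undefined.

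The size depends on the rule eventually used. If any win at 5% counts, the familywise error is 9.75% for two independent tests and at most 14.3% for three, or about 12% to 14% with correlated burden tests. If all must win, error is not inflated, but power for burden at both times alone is about 71% to 80%, taking 84% at each. These figures assume two-sided 5% tests, with emergency care tested once and independently of burden.

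The 84% should not be called wrong. It is conditional on unstated inputs and does not extend to emergency care. Given the Stage 1 design, this should be corrected, but it does not invalidate the trial.

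**What to change.** Add to the SAP:
- One confirmatory test: the arm difference in burden over both follow-ups, from a repeated-measures model adjusted for baseline burden, at two-sided 5%.
- Emergency care tested next in fixed sequence, claimed only if burden is significant, with its definition and analysis period stated.
- Burden effects at 3 and at 6 months reported as supportive.

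Fixed sequence keeps familywise error at 5% without splitting alpha, so the burden test keeps its full level and needs no extra participants.

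Restate the power as applying to burden only and as a difference between arms, giving the SD, alpha and correlation used, computed for the model adopted. If that cannot be done, give 0.67 SD with 40 per arm and label it as the unadjusted single-time figure.

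The cost is more than wording, because the SAP must gain an arm comparison it now lacks, and there can be no formal emergency-care claim if burden is not significant. The SAP is dated January 2022, after the planned end of data collection in March 2021. It should therefore say whether outcome data by arm had been seen when the rule was set; if they had, the analysis should be labelled accordingly.
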